2.7.2 Sample Size

Our estimates of necessary sample size and the associated powers are presented in Appendix A. The sample sizes and associated powers are presented for each of the primary outcome measures. Given these assessments, we have chosen to recruit 30 patients.

2.8 Drug Supply Requirements

Nine nights each of suvorexant 20 mg and matching placebo will be required for each participant with the total study sample being 30. (270 suvorexant 20 mg and 270 placebo). In addition accounting for a 10% dropout rate we anticipate a total need for 300 20 mg suvorexant and 300 placebos

2.9 Adverse Event Reporting

Adverse events (AE) will be collected and reported to the study sponsor and the HFHS IRB as blinded events quarterly. Serious adverse events (SAEs) will be reported as unblinded events to the study sponsor, the HFHS IRB and the FDA. SAEs will be reported within 48 hrs of becoming aware of the event. Initial reports will be followed by reports of the resolution of the SAE.

2.12 Publication Plan

The PI and Col will be responsible for analyses and paper preparation. The paper will submitted to the study sponsor Merck for approval prior to submission for publication.

APPENDIX A

Sample Size and Power Estimates

All estimates based on two-tailed tests with alpha set at 0.05

Nocturnal Polysomnographic (NPSG) Sleep Efficiency (SE)

Based on a SE increase of 8% versus placebo with 20 mg suvorexant in primary insomnia (Herring et al, Neurology 2012;79:2265-2273).

Paired t-test with Alternative 'not equal'

Expected Difference	:	8.000
Standard Deviation of Difference	:	12.800
Effect Size	:	0.625
ALPHA	:	0.050
Sample Size: Low	:	20
Sample Size: High	:	30
Increment	:	1

Sample Size (Per Cell)	POWER
20	0.755
21	0.778
22	0.798
23	0.817
24	0.834
25	0.850
26	0.865
27	0.878
28	0.890
29	0.901
30	0.911

Based on a SE increase of 6% versus placebo with 10 mg zolpidem in primary insomnia (Randall et al, Sleep 2012;35:1551-1557).

Expected Difference	:	6.000
Standard Deviation of Difference	:	9.000
Effect Size	:	0.667
ALPHA	:	0.050
Sample Size: Low	:	20
Sample Size: High	:	30
Increment	:	1

Sample Size	POWER
(Per Cell)	
20	0.807
21	0.828
22	0.846
23	0.863
24	0.878
25	0.892
26	0.904
27	0.915
28	0.925
29	0.934
30	0.942

Sample Size and Power Estimates

All estimates based on two-tailed tests with alpha set at 0.05

Nocturnal Polysomnographic (NPSG) Wake after Sleep Onset (WASO)

Based on a WASO reduction of 25 min versus placebo with 20 mg suvorexant in primary insomnia (Herring et al, Neurology 2012;79:2265-2273).

Paired t-test with Alternative 'not equal'

Expected Difference	:	25.000
Standard Deviation of Difference	:	45.000
Effect Size	:	0.556
ALPHA	:	0.050
Sample Size: Low	:	20
Sample Size: High	:	30
Increment	:	1

Sample Size (Per Cell)	POWER
20	0.655
21	0.678
22	0.700
23	0.721
24	0.741
25	0.760
26	0.777
27	0.794
28	0.809
29	0.823
30	0.837

Based on a WASO reduction of 20 min versus placebo with 10 mg zolpidem in primary insomnia (Randall et al, Sleep 2012;35:1551-1557).

Expected Difference	:	20.000
Standard Deviation of Difference	:	43.000
Effect Size	:	0.465
ALPHA	:	0.050
Sample Size: Low	:	20
Sample Size: High	:	30
Increment	:	1

Sample Size	POWER
(Per Cell)	
20	0.506
21	0.527
22	0.548
23	0.569
24	0.588
25	0.607
26	0.625
27	0.643
28	0.660
29	0.677
30	0.692

Sample Size and Power Estimates

All estimates based on two-tailed tests with alpha set at 0.05

Multiple Sleep Latency Test (MSLT)

Based on reduction in MSLT in Fibromyalgia patients following 1 night of 4 hrs time in bed (i.e. reflects sensitivity of MSLT to sleep time manipulations) relative to their baseline "hyperaroused" MSLT (Roehrs et al, J Psychosom Res 2015:79:27-31)

Paired t-test with Alternative 'not equal'

Expected Difference	:	4.300
Standard Deviation of Difference	:	4.800
Effect Size	:	0.896
ALPHA	:	0.050
Sample Size: Low	:	20
Sample Size: High	:	30
Increment	:	1

Sample Size (Per Cell)	POWER
20	0.967
21	0.974
22	0.979
23	0.984
24	0.987
25	0.990
26	0.992
27	0.994
28	0.995
29	0.996
30	0.997

Based on increase in MSLT in "sleepy" volunteers after 4 nights of 1 hr increased sleep per night (Roehrs et al, Sleep 2012;35:1667-1672)

Expected Difference	:	4.500
Standard Deviation of Difference	:	3.800
Effect Size	:	1.184
ALPHA	:	0.050
Sample Size: Low	:	20
Sample Size: High	:	30
Increment	:	1

Sample Size (Per Cell)	POWER
20	0.999
21	0.999
22	1.000
23	1.000
24	1.000
25	1.000
26	1.000
27	1.000
28	1.000
29	1.000
30	1.000

Finger Withdrawal Latency (FWL)

Based on increase in FWL (i.e. reduction in pain sensitivity) in "sleepy" volunteers after 4 nights of 1 hr increased sleep per night (Roehrs et al, Sleep 2012;35:1667-1672

Paired t-test with Alternative 'not equal'

Expected Difference	:	2.600
Standard Deviation of Difference	:	2.500
Effect Size	:	1.040
ALPHA	:	0.050
Sample Size: Low	:	20
Sample Size: High	:	30
Increment	:	1

Sample Size (Per Cell)	POWER
20	0.993
21	0.995
22	0.996
23	0.997
24	0.998
25	0.999
26	0.999
27	0.999
28	1.000
29	1.000
30	1.000

Estimating greater variability in a Fibromyalgia sample

Expected Difference	:	2.600
Standard Deviation of Difference	:	3.500
Effect Size	:	0.743
ALPHA	:	0.050
Sample Size: Low	:	20
Sample Size: High	:	30
Increment	:	1

Sample Size (Per Cell)	POWER
20	0.883
21	0.899
22	0.913
23	0.926
24	0.936
25	0.945
26	0.953
27	0.960
28	0.966
29	0.971
30	0.976

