2.1 Objectives and Hypotheses

2.1.1 The primary objectives of this proposed study in persons with fibromyalgia and comorbid insomnia are:

1) to assess the effect of suvorexant 20 mg versus placebo on polysomnographic (PSG) measures of sleep.

2) to assess the effect of suvorexant 20 mg versus placebo on next day measures of sleepiness/fatigue.

3) to assess the effect of suvorexant 20 mg versus placebo on next day measures of nociception and pain.

2.1.2 The clinical hypotheses to be tested are:

1) relative to placebo suvorexant 20 mg will increase PSG sleep efficiency and reduce sleep latency and wake after sleep onset in persons with fibromyalgia and comorbid insomnia.

2) relative to placebo suvorexant 20 mg will reduce self-reported next-day pain and nociceptive sensitivity as measured by Finger Withdrawal Testing (FWT) in persons with fibromyalgia and comorbid insomnia.

3) relative to placebo suvorexant 20 mg will reduce self-reported next-day fatigue and normalize Multiple Sleep Latency Test (MSLT) scores in persons with fibromyalgia and comorbid insomnia.

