2.7.1 Statistics

The primary PSG efficacy variables will be sleep efficiency and WASO computed as a mean of nights 7 and 8. The secondary PSG measures will include nocturnal sleep latencies and sleep stages. The primary daytime measures will be the MSLT scores from day 8 and the FWL test results (the average of the am and pm tests) from day 1 and day 8. Secondary daytime measures will include the in-lab self-ratings of sleepiness/fatigue and pain. Another set of secondary measures will be the morning ratings of sleep and previous day's pain collected on the internet administered questionnaires during each 9 day treatment condition. The in-lab sleep, daytime sleepiness/fatigue, and pain data for each dependent variable of the two 9 day conditions will be compared using two factor MANOVAs with drug (suvorexant vs placebo) and days (7 and 8) as the two repeated factors. The internet questionnaire data will be treated similarly using drug and days as two repeated measures. In addition we will conduct path

analyses to determine the degree to which the change in nociceptive sensitivity is mediated directly by suvorexant and indirectly by suvorexant's effect on sleep.

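### FWL has no single primary test and hypothesis 1 has no rule for combining sleep efficiency and WASO; the MSLT and FWL powers are not powers for a drug effect

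*Combined protocol and SAP*

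**What the plan says.** Section 2.7.1 sets the primaries in two sentences: "The primary PSG efficacy variables will be sleep efficiency and WASO computed as a mean of nights 7 and 8", and "The primary daytime measures will be the MSLT scores from day 8 and the FWL test results", the latter averaged over morning and afternoon tests and taken from days 1 and 8. Each dependent variable then gets a two-factor MANOVA with drug and "days (7 and 8) as the two repeated factors".

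Section 2.5.3 defines the primary FWL measure differently, as a mean latency at each of five heat intensities. The schedule at the end of section 2.4.2 places FWL on days 1 and 8 and MSLT on day 8 only.

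Section 2.1.2 poses three hypotheses. The first is that "relative to placebo suvorexant 20 mg will increase PSG sleep efficiency and reduce sleep latency and wake after sleep onset". The second concerns self-reported pain and FWL. The third is that the drug will "reduce self-reported next-day fatigue and normalize Multiple Sleep Latency Test (MSLT) scores". Each joins primary variables to a measure that section 2.7.1 makes secondary: "The secondary PSG measures will include nocturnal sleep latencies and sleep stages" and "Secondary daytime measures will include the in-lab self-ratings of sleepiness/fatigue and pain".

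Appendix A gives paired t-test powers, one outcome at a time, under the heading "All estimates based on two-tailed tests with alpha set at 0.05". SE and WASO use suvorexant and zolpidem differences from placebo. Both MSLT tables and both FWL tables use changes after restricted or extended sleep, and say so. Section 2.7.2 chooses 30 patients.

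**The concern.** A primary conclusion needs one test, or a stated rule for combining several. Hypothesis 2 lacks the single test: the documents give five FWL intensities, two days, and a model whose days do not match, while Appendix A powers one FWL difference. Hypothesis 1 lacks the rule: two primary variables are joined by a conjunction in the hypothesis, but the analysis section does not say whether both must reach significance. In either case the choice could be made after the data are seen, and the error rate and power depend on that choice.

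The power tables raise a different issue. Section 2.7.2 presents Appendix A as the power for each primary outcome. A reader who sees 0.997 for MSLT and 0.976 for FWL may take hypotheses 2 and 3 as nearly certain to be detected if true. Those figures show how sensitive the tests are to sleep time, not the power for suvorexant against placebo.

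**Working it through.** **1. Reproducing Appendix A at n=30.** Two-sided paired t-test, alpha 0.05, df = 29, critical value 2.045. Power comes from the noncentral t with δ = (difference / SD of difference) × √30.

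| Outcome | Difference / SD | δ | Computed | Appendix A |
|---|---|---|---|---|
| SE, suvorexant | 8 / 12.8 | 3.42 | 0.911 | 0.911 |
| SE, zolpidem | 6 / 9 | 3.65 | 0.942 | 0.942 |
| WASO, suvorexant | 25 / 45 | 3.04 | 0.837 | 0.837 |
| WASO, zolpidem | 20 / 43 | 2.55 | 0.692 | 0.692 |
| MSLT, restriction | 4.3 / 4.8 | 4.91 | 0.997 | 0.997 |
| MSLT, extension | 4.5 / 3.8 | 6.49 | 1.000 | 1.000 |
| FWL, extension | 2.6 / 2.5 | 5.70 | 1.000 | 1.000 |
| FWL, larger SD | 2.6 / 3.5 | 4.07 | 0.976 | 0.976 |

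The arithmetic in Appendix A is correct.

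**2. Can the stated model be run?**

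| Variable | Days measured (2.4.2) | Days taken as primary (2.7.1) | Days in model (2.7.1) |
|---|---|---|---|
| SE, WASO | nights 7, 8 | mean of nights 7, 8 | 7, 8 |
| MSLT | day 8 | day 8 | 7, 8 |
| FWL | days 1, 8 | days 1, 8 | 7, 8 |

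No day 7 value is scheduled for MSLT or FWL, so the model as written cannot be fitted to either.

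**3. FWL error if several tests can count.** With k independent tests at 0.05 the chance of at least one false positive is 1 − 0.95^k.
- Five intensities: 1 − 0.95^5 = 0.226.
- Ten intensity-by-day tests: 1 − 0.95^10 = 0.401.

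The documents give no correlations. In a null simulation at n=30 with an assumed common correlation of 0.8, these fall to about 0.13 and 0.18. The ranges are therefore 13% to 23% and 18% to 40%.

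**4. Hypothesis 1.** SE is sleep time over time in bed (section 2.4), and time in bed is fixed at 8 hours (section 2.5.1), so SE and WASO should be strongly related. Correlations of 0.8 to 0.9 are assumed.
- Either suffices: 1 − 0.95² = 0.0975 if independent; about 0.079 at 0.8 and 0.071 at 0.9 by simulation.
- Both required: no inflation. Joint power at n=30 is 0.911 × 0.837 = 0.76 if independent, 0.81 at 0.8 and 0.83 at 0.9. On the zolpidem inputs it is 0.942 × 0.692 = 0.65 if independent, rising to 0.69.
- Holm across the two: SE 0.86 to 0.90, WASO 0.81 to 0.82.

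**5. MSLT and FWL at half the stated difference (assumed), n=30, alpha 0.05.**
- MSLT: 2.15 / 4.8 × √30 = 2.45, power 0.66. On the other source, 2.25 / 3.8 × √30 = 3.24, power 0.88.
- FWL: 1.3 / 3.5 × √30 = 2.03, power 0.50. With SD 2.5, δ = 2.85, power 0.79.
- Differences giving 80% power: about 2.54 min for MSLT (SD 4.8) and 1.85 s for FWL (SD 3.5).

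A half-sized effect is not extreme on the plan's own figures. If the SE gains of 8% and 6% are percentage points of 480 minutes (an assumption), they are 38.4 and 28.8 minutes of extra sleep. The extension source used 60 minutes, so the ratios are 0.64 and 0.48. Linear scaling from these is only an illustration.

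**The case against.** The strongest reply on hypothesis 1 is that its wording already asks for both SE and WASO to move, which needs no alpha split. That is the natural reading, and the fix adopts it. But the same sentence also requires sleep latency, which section 2.7.1 makes secondary, so the wording cannot serve as the decision rule unaided.

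On FWL, a sponsor may say that a MANOVA handles several days or intensities in one test. It could, but section 2.7.1 names only drug and days as factors, gives the wrong days for FWL, and does not mention intensity.

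On the effect sizes, Appendix A discloses each source, and the first MSLT table describes itself as showing sensitivity to sleep time. The plan's rationale is that better sleep reduces pain, so these sources are relevant, and one FWL table already allows for greater variability. All of this stands. It also stands that MSLT and FWL do not drive the sample size; WASO is the limiting outcome.

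A reader might infer that any one of the four primaries would make the trial positive, and so call for a correction across all four. The documents do not support this: section 2.1.2 sets out three separate hypotheses, and no section says that one success among four is enough. Nor do they show that the drug effect on MSLT or FWL is smaller than the borrowed one; they give no drug effect for either.

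**Conclusion.** The concern holds in limited form. Testing each of three separate hypotheses at two-sided 0.05 is acceptable. What is missing is a defined test within two of them.

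- **FWL:** the sections conflict, and the stated model cannot be run for FWL or MSLT. The 13% to 23% (five tests) and 18% to 40% (ten tests) apply only if each is tested at 0.05 and any one counts. The plan does not say it will do this, but nothing in it rules it out.
- **Hypothesis 1:** about 7% to 8% error if either variable suffices, at assumed correlations of 0.8 to 0.9; no inflation if both are required, with joint power 0.76 to 0.83 on the suvorexant inputs.
- **Power tables:** correctly computed and openly sourced, but the MSLT and FWL rows are not power for a drug effect. The 0.66 and 0.50 rest on an assumed halving with SDs 4.8 and 3.5.

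The direction of the two MSLT sources (one a fall, one a rise) does not alter a two-sided power. It does matter for interpretation, because the plan does not say which direction counts as normalizing.

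**What to change.** 1. In section 2.7.1, state that the three hypotheses are separate claims, each judged on its own primary variable or variables, and that the other measures named in section 2.1.2 are supportive. For hypothesis 1, require both SE and WASO at two-sided 0.05, and give the joint power in Appendix A (0.76 if independent, 0.81 to 0.83 at assumed correlations of 0.8 to 0.9). Holm across the two is an acceptable alternative.
2. Name one primary FWL summary and make sections 2.5.3 and 2.7.1 agree. An example is the mean over the five intensities and both test times on day 8, compared between treatments, with day 1 and single intensities secondary. Keep the days 7 and 8 factor for PSG only, and write the correct model for MSLT and FWL. Section 2.5.1 gives the PSG study nights as 8 and 9, so it must be reconciled with sections 2.4.2 and 2.7.1.
3. State which direction of change in MSLT supports hypothesis 3. The elevated latencies described in section 2.2 imply a decrease.
4. Add one reduced-effect power row each for MSLT and FWL to Appendix A, marked as assumed.

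The cost is text only, with no change in sample size. The stated power for hypothesis 1 falls from 0.911 and 0.837 separately to 0.76 to 0.83 jointly, and Appendix A will show less favourable MSLT and FWL figures beside the present ones.
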